5.1.1 Screening phase

Upon giving written informed consent, subjects will enter the screening phase to determine eligibility. Subject screening procedures will take place within 35 days prior to start of treatment. During the screening phase, the subject will undergo safety and other assessments to determine eligibility for the study.

Subjects must have at least 16 weeks of transfusion history available immediately preceding and including the date of the first administration of IMP in this study. Transfusion data should include the type of transfusion (e.g., RBC, platelets), number of units, and date of transfusion. RBC transfusion data should include the Hb value for which the transfusion was administered (i.e., pre-transfusion Hb value).

5.1.2 Primary phase of the treatment period ()

Imetelstat sodium will be administered at a dose of . Subjects will receive imetelstat on day of each day treatment cycle. Also see VII Schedule of assessments and procedures (part 1).

Best supportive care (BSC) may be used in combination with imetelstat when clinically indicated per investigator. BSC includes, but is not limited to, treatment with transfusions, antibiotic, antiviral, and/or antifungal therapy as well as nutritional support as needed.

Subjects will receive imetelstat for at least the first after the date of first dose, unless the subject experiences unacceptable toxicities, withdraws consent, or meets any other treatment discontinuation criteria as described in section 7.7.

5.1.3 Disease assessments in the primary phase of the treatment period (■■■■■)

After cycles ■ and ■ (i.e., at the beginning of cycles ■ and ■) response assessments will be carried out based on bone marrow and peripheral blood samples taken. For that, blood counts to assess potential cytopenias will be carried out and bone marrow and peripheral blood smears will be prepared to perform cytomorphology assessments.

Of these response assessments, the assessment at the end of ■■■■■ (performed at the beginning of cycle 5) is the primary endpoint (pEP) assessment.

Based on the outcome of the disease assessment in ■■■■■, if signs of disease progression are seen in the bone marrow, treatment with imetelstat will be stopped and the patient will undergo EOT and enter the follow-up phase.

Based on the outcome of the pEP (■■■■■) visit disease assessment, subjects will be either discontinued from treatment with imetelstat and enter the posttreatment follow-up phase (non-responders) or will continue treatment with imetelstat until loss of response/disease progression in the extension phase of the treatment period (responders) (see below at 5.1.4). In the absence of alternative treatment options, non-responders with stable or controlled disease may continue treatment in the extension phase at the investigator's discretion, in consultation with the sponsor, provided the disease remains controlled and none of the discontinuation criteria as described in section 7.7 are met. These subjects will follow the assessments and procedures according to the schedule of assessments for the extension phase (section VII, Part 2c). Responders who have BM blasts $\geq 5\%$ at the response assessment in cycle ■ will continue to receive imetelstat every ■ weeks. Responders who have BM blasts $<5\%$ at the response assessment in cycle ■ will continue to receive imetelstat every ■ weeks.

The disease assessment will be performed according to combined response criteria based on IWG 2018 criteria (MDS)¹ and the criteria of the European LeukemiaNet (AML)² in order to harmonize the criteria for MDS and AML patients in this trial. The combined criteria are listed in Appendix III a), section 16.3.

- Evidence of clinical benefit is defined as:
 - **At least partial remission (PR):**
 - This includes CR, CRi, PR and HI (any line) as per the combined response criteria used in this trial

All other assessment outcomes will result in treatment discontinuation. MLFS will be recorded but is not a criterion for treatment continuation. The corresponding patients (=non-responders) will then undergo the EOT visit and the follow-up period. As described above, in the absence of alternative treatment options, non-responders with stable or controlled disease may continue treatment in the extension phase at the investigator's discretion, in consultation with the sponsor. These subjects will follow the assessments and procedures according to the schedule of assessments for the extension phase (section VII, Part 2c).

Patients with at least PR at this pEP assessment will continue in the extension phase described below in section 5.1.4.

A risk/benefit assessment is to be performed when ■ patients have started treatment, of which at least ■ patients have completed ■ full cycles of imetelstat (■■■■■■■■■■). Please refer to section 4.2 for more details.

5.1.4 Extension phase of the treatment period (from ■■■■■■■■ 1 on)

Subjects who meet the criteria to remain on treatment after completion of the ■■■■■■■■ disease assessment and have BM blasts $\geq 5\%$ may continue dosing on day ■■■■■■■■ of each ■■■■■■■■ treatment cycle in the extension phase of the treatment period. Subjects who meet the criteria to remain on treatment but have BM blasts $< 5\%$, may continue dosing on day ■ (only) of each ■■■■■■■■ treatment cycle in the extension phase of the treatment period.

Treatment will continue until the subject experiences unacceptable toxicities or shows loss of response/disease progression per the combined disease assessment criteria used in this trial (see Appendix III a), section 16.3), withdraws consent, or meets any other discontinuation criteria defined in section 7.7.

For subjects who continue treatment in the extension phase of the treatment period, each disease assessment should confirm continued clinical benefit and absence of disease progression per the combined disease assessment criteria. For patients exhibiting a response to treatment, each disease assessment will also determine the frequency of imetelstat treatment (once in ■ weeks or once in ■ weeks) based on BM blast levels. Serial measurements of safety and efficacy will be continued on scheduled study visits (see VII Schedule of assessments and procedures [part 2]) in the extension phase of the treatment period. BSC may be continued to be used in combination with imetelstat when clinically indicated per investigator. All subjects who receive at least one dose of imetelstat will undergo end of treatment (EOT) evaluations when imetelstat is discontinued. The reason for discontinuation will be recorded.

Non-responders with stable or controlled disease may continue treatment in the extension phase of the study at the investigator's discretion as described in section 5.1.3. For these subjects, safety and efficacy data may be collected, without impacting the primary study objectives, timelines, or statistical analyses. These subjects will follow the assessments and procedures according to the schedule of assessments for the extension phase (section VII, Part 2c).

5.1.5 Posttreatment follow-up (FU) period

All AEs will be recorded by the investigator from the time the subject signed the ICF until ■■■■■■■■ days after the last dose of IMP. Additionally, all serious AEs (SAEs) made known to the investigator at any time thereafter and are suspected of being related to imetelstat will also be documented. Therefore, at ■■■■■■■■ days the first FU visit will take place. For the second FU visit (=EOS) please refer to VII Schedule of assessments and procedures (part 3).

5.2 End of the clinical study

For this study, the primary outcome will be analyzed after the last patient has completed the study (individual EOS). The end of the study as a whole will be the date when the clean database is available and ready for export for the statistical analyses. However, the primary completion event of the study will be the date of last patient end of study (LPEOS).

5.3 Closure of study sites/premature termination of the clinical study

The sponsor might close this study or parts thereof at any time if

- risk-benefit ratio becomes unacceptable based on safety findings or any interim analysis from this study or upcoming information from other clinical or animal studies
- the study conduct does not suggest a proper completion of the study within a reasonable time frame

The investigator has the right to close his/her center at any time.

All closures should occur only after consultation between sponsor, CPI and study center(s). All affected institutions (e.g., IEC(s), competent authorities, study center) must be informed as applicable according to local law. All study materials (except documentation and research samples taken for correlative studies that have to remain stored at site) must be returned to the sponsor. The investigator will retain all other documents until notification given by the sponsor for destruction.

6 Study population

6.1 Justification of selection criteria

The selection criteria are chosen to ensure that subjects with specific risks for administration of the IMP and / or subjects with conditions which may have an impact on the objectives of the study are excluded.

6.2 Justification of gender selection

Male and female subjects will be included in the present study representing the population of patients suffering from AML / HR MDS without any gender prevalence.

6.3 Inclusion criteria

Subjects must fulfill all of the following criteria before inclusion in the study:

- 1 Signed written informed consent
- 2 Male and female ≥ 18 years at the first screening
- 3 Must be able to adhere to the study visit schedule and other protocol requirements
- 4 Initial diagnosis of AML or MDS according to WHO 2016 classification
- 5 At least one cytopenia (ANC $< \blacksquare/\mu\text{L}$ or platelet count $< \blacksquare/\mu\text{L}$ or hemoglobin $< \blacksquare \text{ g/dL}$)
- 6
 - a. Failure to achieve complete or partial response or hematological improvement observed after at least six azacitidine monotherapy or four decitabine monotherapy based 4-week treatment cycles administered during the past two years
OR
 - b. Failure to achieve complete or partial response or hematological improvement observed after at least two 4-week treatment cycles with azacitidine plus venetoclax or with decitabine plus venetoclax during the past two years

- OR
- c. Relapse after initial complete or partial response or hematological improvement observed after at least six (azacitidine) or four (decitabine) based 4-week treatment cycles administered during the past two years
- OR
- d. Relapse after initial complete or partial response or hematological improvement observed after at least two 4-week treatment cycles with azacitidine plus venetoclax or with decitabine plus venetoclax during the past two years
- OR
- e. Intolerance to treatment with HMA-based therapy during the past two years
- 7 Not eligible for allogeneic stem cell transplantation
- 8 $\geq 5\%$ bone marrow blasts at screening
- 9 Off all other treatments for AML/MDS for at least 14 days; G-CSF and erythropoietin are allowed before and during the study as clinically indicated
- 10 ECOG performance status of 0-2
- 11 Biochemical laboratory test values must be within the following limits:
[REDACTED]
[REDACTED]
[REDACTED]
[REDACTED]
[REDACTED]
- 12 Availability of blood counts and transfusion events for previous 16 weeks
- 13 Women of childbearing potential and practicing a highly effective method of birth control according to the Clinical Trial Facilitation Coordination Group Recommendation (Version 1.1, 2020):
- combined (estrogen and progestogen containing) hormonal contraception associated with inhibition of ovulation:
 - o oral
 - o intravaginal
 - o transdermal
 - progestogen-only hormonal contraception associated with inhibition of ovulation:
 - o oral
 - o injectable
 - o implantable
 - intrauterine device (IUD)
 - intrauterine hormone-releasing system (IUS)
 - bilateral tubal occlusion
 - vasectomised partner
 - sexual abstinence
- For females, these restrictions apply for 3 months after the end of dosing. Note: If the childbearing potential changes after start of the study (e.g., woman who is not heterosexually active becomes active, premenarchal woman experiences menarche) a woman must begin a highly effective method of birth control, as described above
- 14 A woman of childbearing potential must have a negative serum (β -human chorionic gonadotropin [β -hCG] or urine pregnancy test at screening and agree to be tested on day 1 of every cycle and at EOT

- 15 A man who is sexually active with a woman of childbearing potential and has not had a vasectomy must agree to use a barrier method of birth control eg, either condom with spermicidal foam/gel/film/cream/suppository or partner with occlusive cap (diaphragm or cervical/vault caps) with spermicidal foam/gel/film/cream/suppository, and all men must also not donate sperm during the study. For males, these restrictions apply for 3 months after the end of dosing
- 16 France-specific inclusion criterion: Subjects participating at French sites must be covered by the French public welfare system.
- 17 Patients who are relapsed or refractory to, or not eligible for, therapy with approved and available FLT3 or IDH1/IDH2 inhibitors or other approved targeted therapies.

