8.2.1.3 Prior therapies

Prior transfusion history

Transfusion history must be available for at least the 16 weeks immediately preceding and including the date of the first IMP administration. Transfusion data should include the type of transfusion (e.g., RBC, platelets), number of units, reason and date of transfusion.

Transfusion data should also include the pretransfusion Hb levels that triggered the RBC transfusions. For platelet transfusions, data should include the platelet value for which the platelet transfusion was administered.

All RBC transfusion events during the 16 weeks immediately preceding and including the date of first administration of the IMP should be recorded (including any transfusions at outside local institutions). RBC transfusions administered for elective surgery will not be relevant for meeting RBC transfusion inclusion criteria requirements, but should still be recorded in the eCRF.

The RBC transfusion data during the 16 weeks immediately preceding the first administration of IMP will be used to determine the baseline RBC transfusion requirement (necessary for HI-E assessment) for an individual study subject.

As mentioned above (in 8.2.1.2), prior AML/MDS specific treatments will be recorded. The following information will be captured:

- type of HMA (azacitidine or decitabine)
- number of total HMA cycles received
- best response with HMA according to IWG (MDS) / ELN (AML) criteria
- number of cycles until best response
- duration of response

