Progressive disease (PD)	Evidence for an increase in bone marrow blast percentage and/or increase of absolute blast counts in the blood: 
 >50% increase in marrow blasts over baseline (a minimum 15%-point increase is required in cases with <30% blasts at baseline; or persistent marrow blast percentage of >70% over at least 3 mo; without at least a 100% improvement in ANC to an absolute level ($>0.5 \times 10^9/L$ [500/μL], and/or platelet count to $>50 \times 10^9/L$ [50 000/μL] non-transfused); or >50% increase in peripheral blasts (WBC x % blasts) to $>25 \times 10^9/L$ (>25 000/μL) (in the absence of differentiation syndrome)†; or New extramedullary disease
Hematologic relapse (after CR, CR _i)	Bone marrow blasts $\geq 5\%$; or reappearance of blasts in the blood; or development of extramedullary disease
Hematologic improvement (HI)	
Erythroid response (HI-E)	
NTD (0 RBCs in 16 wk)*	At least 2 consecutive Hb measurements ≥ 1.5 g/dL for a period of minimum 8 wk in an observation period of 16 to 24 wk compared with the lowest mean of 2 Hb measurements (apart from any transfusion) within 16 wk before treatment onset‡; only a response duration of at least 16 wk, however, is considered clinically meaningful
LTB (3-7 RBCs in 16 wk in at least 2 transfusion episodes, maximum 3 in 8 wk)*	Transfusion independence, defined by the absence of any transfusions for at least 8 wk in an observation period of 16-24 wk with the same transfusion policy (defined below) compared with 16 wk prior to treatment; only a response duration of at least 16 wk, however, is considered clinically meaningful
HTB (≥ 8 RBCs in 16 wk, ≥ 4 in 8 wk)	
Major response: Major HI-E response in HTB patients corresponds to transfusion independence, defined by the absence of any transfusions over a period of minimum 8 wk in an observation period of 16-24 wk with the same transfusion policy (defined below) compared with 16 wk prior to treatment; only a response duration of at least 16 wk, however, is considered clinically meaningful
 
Minor response: Minor HI-E response in HTB patients is defined as a reduction by at least 50% of RBCs over a minimum of 16 wk with the same transfusion policy (defined below) compared with 16 wk prior to treatment

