Platelet response (HI-P) (pretreatment, $< 100 \times 10^9/L$)	
 Absolute increase of $30 \times 10^9/L$ for patients starting with $>20 \times 10^9/L$ PLTs or Increase from $<20 \times 10^9/L$ to $>20 \times 10^9/L$ and by at least 100% 
In addition,
 
 Evolution of bleeding symptoms is to be taken into account Increments of platelets also for patients with a pretreatment PLT count of $>100 \times 10^9/L$ are to be reported
Neutrophil response (HI-N) (pretreatment, all patients)	
 At least 100% increase and an absolute increase $>0.5 \times 10^9/L$ (pretreatment, $<1.0 \times 10^9/L$) Increments of neutrophils also for patients with a pretreatment ANC of $>1.0 \times 10^9/L$ are to be reported
Progression or relapse after HI†	
At least 1 of the following:
 
 At least 50% decrement from maximum response levels in granulocytes or platelets Reduction in Hb by ≥ 1.5 g/dL Transfusion dependence

†Certain targeted therapies, for example, those inhibiting mutant IDH proteins, may cause a differentiation syndrome, that is, a transient increase in the percentage of bone marrow blasts and an absolute increase in blood blasts; in the setting of therapy with such compounds, an increase in blasts may not necessarily indicate PD.

b) IWG 2023 response criteria for HR-MDS

For secondary endpoint and MDS population only

RESPONSE	DEFINITION
Complete remission (CR)	
 BM: $<5\%$ myeloblasts*; dysplasia may persist PB: Hb ≥ 10 g/dL, platelets $\geq 100 \times 10^9/L$; neutrophils $\geq 1.0 \times 10^9/L$; blasts $0\%^\dagger$
CR equivalent*	
Patients with $<5\%$ BM blasts at baseline:
 
 BM: $<5\%$ myeloblasts*; dysplasia may persist PB: Hb ≥ 10 g/dL, platelets $\geq 100 \times 10^9/L$; neutrophils $\geq 1.0 \times 10^9/L$; blasts $0\%^\dagger$ Full cytogenetic clearance of baseline abnormalities (complete cytogenetic response)
Partial remission (PR)	
All CR criteria except:
 
 BM blasts decreased by $\geq 50\%$ over pretreatment but still $\geq 5\%$ Cellularity and morphology not relevant

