## 6.2 Endpoints and Related Variables

### 6.2.1 Primary Endpoint

Objective	Endpoint
To assess the efficacy of imetelstat for the treatment of AML and MDS patients failing or being refractory to first line hypomethylating agent (HMA)-based treatment	Overall hematological response rate as assessed in week ████████ of treatment with imetelstat using the combined response assessment criteria for MDS and AML (see Appendix 11.2 for more details). The main analysis will be based on the eCRF item “Is the subject classified to be a Responder according to protocol?” (RS_DSRESP).

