## 7.3 Data Review

Data are checked and cleaned during the course of the study. Protocol deviations such as time window deviations are identified during monitoring and by data management checks. The statistical programmer will collect the protocol deviations. Additional protocol deviations might be identified and added during this data review.

Classification of protocol deviations into critical and non-critical will be discussed between Sponsor and statistician prior to database lock, with the final decision being made by the Sponsor. A critical protocol deviation is defined as protocol deviation which might influence the outcome of the primary analysis (e.g., a violation of eligibility criteria detected after enrolment). The free choice of subjects to terminate their study participation prematurely is described in the study protocol and thus not regarded as protocol deviation but as reason for exclusion from the per protocol set. The following list of criteria can be used to identify critical protocol deviations and is not meant to be exhaustive:

- Violation against eligibility criteria
- Deviation from visit window of primary endpoint visits.
- Assessment of primary endpoint not performed
- Use of disallowed concomitant medication

For further details it is referred to the Data Review Meeting Plan (DRM).

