### 8.3 Evaluation of Primary Endpoint

The primary objective of this study is to assess the efficacy of imetelstat for the treatment of AML and MDS patients failing or being refractory to first line hypomethylating agent (HMA)-based treatment. This should be illustrated by testing the hypothesis stated in section 2.5 using the primary endpoint stated in section 6.2.1 (see 7.7.4 for derivation).

The absolute and relative frequencies of overall hematological response as assessed in week ■ (beginning of ■) of treatment with imetelstat will be evaluated using the FAS and repeated for the PPS if the analysis sets differ more than 10% between the number of included subjects. Treatment success will be determined by patients showing at least PR (CR, CRi or PR) and/or showing a hematologic improvement for one or several lines.

The primary analysis will be based on a Simon's two-stage design for an initial assessment of efficacy. Based on the study hypothesis (see section 2.5), an absolute cut-off value of ■ subject out of ■ will be used to determine if the study must be stopped for futility at the IA. For the final analysis in case the study proceeds, if final sample size is equal to the calculated one, a cut-off value of ■ subjects out of ■ will be fixed.

If final sample size is different from the calculated sample size (overrunning), uniformly minimum variance unbiased estimator UMVUE will be tested (see Melikov M. & Karanevich A. 2022) with a

model based on a binomial distribution conditioned to the first stage results and with an assumed expected true response rate of 0.2.

A SAS macro (based on source <https://www.lexjansen.com/pharmasug/2022/SA/PharmaSUG-2022-SA-123.pdf>) can be used for this analysis (see Appendix 11.4)

For the IA:

A binomial exact test will be performed with a two-sided 90% confidence interval for overall hematological response rate using the Clopper-Pearson method. A SAS pseudo code can be:

```
proc freq data=Data;
  tables Hematological_response / binomial(all level="0") alpha=0.1 cl ;
  exact binomial /point;
run;
```

For the final analysis:

The final analysis was going to be performed with a calculation of the p-value and a 90% confidence interval (two-sided, equivalent to a one-sided 95% confidence interval) for the UMVUE (see Melikov M. & Karanevich A. 2022).

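### The protocol both allows and prohibits erythropoietin on study; separately, the visible HI-P and HI-N criteria carry no transfusion or G-CSF condition, which a supplementary response rate would cover cheaply

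*Protocol*

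**What the plan says.** **ESA rule.** Protocol 6.3, inclusion criterion 9 (repeated in the synopsis), says that "G-CSF and erythropoietin are allowed before and during the study as clinically indicated". Protocol 16.7 (Appendix VII) puts ESA therapy first in its list of medications prohibited during the study. That list spells out qualifications for corticosteroids but none for ESAs.

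**Deviations.** SAP 7.3 names "Use of disallowed concomitant medication" among the criteria that can identify a critical protocol deviation. SAP 4.1.2 removes patients with major deviations from the PPS.

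**Endpoint.** Under Protocol 2.3.1 and SAP 7.7.4, haematologic improvement in a single line makes a patient a responder without CR, CRi or PR. SAP 6.2.1 adds: "The main analysis will be based on the eCRF item" in which the investigator records responder status (RS_DSRESP).

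**HI criteria.** In Protocol Appendix III a), reproduced in SAP Appendix 2 a), HI-N asks for "At least 100% increase and an absolute increase" of more than 0.5 x 10^9/L. HI-P asks for a rise of 30 x 10^9/L, or at least a doubling from below to above 20 x 10^9/L. Neither visible row mentions platelet transfusion or G-CSF.

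**Permitted support.** Criterion 9 allows G-CSF. Protocol 5.1.2 allows best supportive care, including "treatment with transfusions, antibiotic, antiviral, and/or antifungal therapy".

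**The concern.** The two ESA statements cannot both be followed. An investigator who reads the eligibility section may give erythropoietin; one who reads the appendix may not. If practice differs between sites, haemoglobin and red-cell transfusion need are measured under different background treatment, and HI-E depends on both. At data review, the same patient is compliant under one text and a user of prohibited medication under the other.

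The HI-P and HI-N rows raise a related question. A platelet count taken soon after a transfusion, or a neutrophil count raised by G-CSF, can literally satisfy the visible wording. If the investigator does not discount it, supportive care is counted as response to imetelstat, both in the reported rate and in the decision to continue treatment. SAP 8.3 plans no response summary that separates such patients.

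**Working it through.** The plan gives no figure on this point, so the check is mainly a comparison of texts, followed by a scale calculation.

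**Step 1: ESA texts side by side.**

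| Place | Erythropoietin/ESA on study |
|---|---|
| Protocol synopsis and 6.3, criterion 9 | Allowed as clinically indicated |
| Protocol 16.7, Appendix VII | Prohibited, no exception printed |

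Erythropoietin is an erythropoiesis-stimulating agent, so the conflict is direct. The body of Protocol 7.9.3 (concomitant medications) is not visible, but nothing there could make these two statements agree as they stand.

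**Step 2: guards within the response table (Protocol Appendix III a)).**

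| Row | Transfusion or growth-factor condition in the visible text |
|---|---|
| HI-E | Haemoglobin measured apart from transfusion, or transfusion independence or reduction |
| PD | Platelet recovery must be on a non-transfused count |
| HI-P | None |
| HI-N | None |

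Protocol 8.2.1.3 also says that baseline red-cell data "will be used to determine the baseline RBC transfusion requirement (necessary for HI-E assessment"; the visible text has no matching statement for platelets and HI-P.

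**Step 3: what the investigator must consult.** Protocol 8.1.5 requires transfusion information between enrolment and visit 9 for the primary assessment. Protocol 8.1.6 asks for all transfusion information before each disease assessment is completed. Protocol 8.2.4 names transfusion assessment as part of response assessment. Protocol 8.2.4.2 collects platelet transfusions, with dates and trigger platelet values, for HI assessment in general. These put the data in front of the investigator; in the visible text they do not say how the data alter HI-P.

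**Step 4: scale of one HI-only response.** The size of cohort 2 is blacked out, so n is an assumption; 10, 20 and 30 are shown. One response adds 1/n to the rate. The planned interval is the two-sided 90% Clopper-Pearson interval (Protocol 10.8.1, SAP 8.3): lower limit = Beta(0.05; x, n-x+1), upper limit = Beta(0.95; x+1, n-x). With x = 0 the lower limit is 0 and the upper limit is 1 - 0.05^(1/n); for n = 20, 1 - 0.05^(1/20) = 13.9%.

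| Assumed n | Added by one response | Interval at 0 responders | Interval at 1 responder |
|---|---|---|---|
| 10 | 10 points | 0 to 25.9% | 0.5 to 39.4% |
| 20 | 5 points | 0 to 13.9% | 0.3 to 21.6% |
| 30 | 3.3 points | 0 to 9.5% | 0.2 to 14.9% |

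This shows what one reclassified patient would do to the report. It does not estimate how often that happens; the documents give no frequency for HI produced by G-CSF, ESA or platelet transfusion.

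**The case against.** On the ESA conflict, the defence is that it matters little. SAP 7.3 offers its list as an aid, the sponsor classifies deviations before lock, and PPS membership is decided per subject, so exclusion is not automatic. The section speaks of critical deviations and the PPS definition of major ones. The FAS is primary, and an ESA user stays in it. All of this stands and limits the consequence. It does not remove the conflict, and case-by-case classification still needs to know which rule applied. A reader might also infer that the PPS result appears only when enough patients are excluded, since SAP 8.3 has the analysis "repeated for the PPS if the analysis sets differ more than 10% between the number of included subjects". Protocol 10.8.1 repeats it on the PPS without that condition, so no threshold argument should be built on the SAP sentence alone.

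On HI, the case is stronger. Transfusion is a stated input to response assessment, and an experienced haematologist may well discount a transfused platelet count or a G-CSF-driven neutrophil count. The table refers to a transfusion policy defined below it and carries footnote markers whose text is not visible; with 7.9.3, these are places where a rule could sit. Response, medication and transfusion listings are planned, so individual cases could be checked by hand. This stands far enough that the second half is a possible risk, not a demonstrated error.

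A reader might infer that the effect falls mainly on cohort 2: the SAP document history reports no responders at the interim analysis, and Protocol 1.3.1 and 7.2.2.1 link denser dosing to more cytopenia. The documents do not support that conclusion. Both supports were open to cohort 1 as well. Zero responders under a definition that counted HI would be evidence against the mechanism; under the earlier continuation rule of PR, CR or CRi (Protocol 7.1.1) it would say nothing about HI. More cytopenia creates more occasion for support but also makes the required count rises harder to reach.

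**Conclusion.** The ESA rule is wrong as written. It affects treatment on study, the background against which HI-E is judged, and the classification of deviations for the PPS. The FAS rate does not depend on how such deviations are classified.

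The HI-P and HI-N point is a cheap improvement. It rests on the visible criteria only. The size and direction of any effect, overall or by cohort, are unknown, and it cannot be said that the reported response rate will be inflated.

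A reader might also note that, for an assumed n of 14 to 21, one response carries the upper 90% limit from below to above 20%, the response rate expected in Protocol 10.3, and infer that a conclusion turns on it. It does not: that rate belongs to the superseded two-stage design, n is assumed, and Protocol 10.1 and 10.8.1 make the analysis exploratory. No formal decision changes. What is at stake is how a small reported response rate is read.

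**What to change.** 1. **ESA rule.** Choose one rule and state it identically in criterion 9, the synopsis and Appendix VII. Either direction is workable; one option is to allow stable use but no start or dose increase on study. Apply that rule when classifying deviations under SAP 7.3. Cost: a short protocol clarification.

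2. **Supplementary response rate.** Keep RS_DSRESP as the main analysis. In SAP 8.3, add a second rate by cohort with its 90% Clopper-Pearson interval. Start from the RS_DSRESP responders and keep every CR, CRi and PR. Keep an HI-only responder only if at least one line qualifies: HI-P without recent platelet transfusion, HI-N without new or increased G-CSF, or HI-E without new or increased ESA. The sponsor sets the windows in advance. Report the number of HI-only responders alongside.

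SAP 2.10 allows this as a SAP update before database lock, because the primary definition is untouched. Platelet transfusion dates are already collected. G-CSF and ESA dates are less certain: in cycles 1 to 4 the schedule has general concomitant medication at screening and once later, and MDS/AML-specific medication at five visits, without saying which entry holds these drugs. The downside is some date queries for HI-only responders and a supplementary rate that may be lower than the main one.
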